9.1.6.2. Missing or Partial Medication Stop Date

References to year and month are the year and month of the stop date:

1. If year and month are known and study medication stopped during that month and year, use the stop date of study medication.
2. If year and month are known and informed consent was provided during that month and year, use the date of informed consent.
3. If year and month are known and study medication stopped after the date of informed consent and not in the month that medication stopped, use the last day of the month.

4. If year and month are known and are prior to the month of informed consent, use the first day of the month.
5. If only year is known and study medication stopped during that year, use the stop date of study medication.
6. If only year is known and study medication stopped after that year, use December 31st of that year.
7. If only year is known and study medication stopped prior to that year, use the first day of the year.
8. Should any of the previous stop dates be created before a start date, either a complete date or an imputed one, use the (imputed) start date instead of the date that would otherwise be created.
9. Otherwise, if stop date is unknown, leave as missing.

9.1.6.3. Missing Severity

If severity is missing for any AE/TEAE, then its severity will be classified as “severe” in the summary tables.

9.1.6.4. Missing Relationship

If the assessment of relationship of the TEAE to study drug is missing, then it will be classified as “related” in the summary tables.

9.2. Clinical Safety Laboratory Data

Laboratory data will be presented using the Système International (SI) unit. Descriptive statistics for clinical safety laboratory data will be presented by treatment group and by visit, starting at the Baseline visit. Analyses will be based on the safety population. Change from baseline and percent change from baseline to post-baseline visit will also be presented. No formal statistical comparisons will be performed. Data will be attributed to visits according to the visit windows in [Table 4](#).

Summary tables by treatment group will be presented for each category of data separately. Routine clinical laboratory data will include hematology, serum chemistry, and urinalysis. Quantitative laboratory test results will be summarized using descriptive statistics (n, mean, SD, median, Q1, Q3, minimum, and maximum). Line plots (for ALT and AST) over time will be provided by treatment group using the mean \pm SE for the change from baseline and percent change from values. Qualitative tests (eg, some urinalysis assessments) will be categorized accordingly. The set of laboratory parameters included in each table will correspond to those requested in the study protocol.

The percentage of subjects with specific treatment-emergent laboratory values that meet pre-defined limits of change (PDLC) will be summarized for these laboratory parameters.

The incidence rates of PDLC values will be compared descriptively between treatment groups, without any statistical testing.

If a subject has even 1 post-baseline value that meets the PDLC criteria for any lab parameter, then all values of that parameter for that subject will be listed.

Table 9: Pre-defined Limits of Change Criteria for Clinical Safety Laboratory Data

Laboratory Test	Parameter for ANY Value and LAST Value
Chemistry	
Albumin	Composite: < LLN and > 25% decrease from BL
Bilirubin	Composite: > ULN and > 25% increase from BL
	Absolute Value: > 2X ULN
Bicarbonate	Absolute Value: < 16 mEq/L
Calcium	Composite: > ULN and > 10% increase from BL
Phosphorus	Composite: < LLN and > 25% decrease from BL
	Composite: > ULN and > 25% increase from BL
Potassium	Composite: < LLN and > 15% decrease from BL
	Composite: > ULN and > 15% increase from BL
Sodium	Composite: < LLN and decrease > 5 mEq/L or more from BL
	Composite: > ULN and increase > 5 mEq/L or more from BL
Uric Acid	Male: absolute value $\geq 624.6 \mu\text{M}$
	Female: absolute value $\geq 505.6 \mu\text{M}$
	Composite: < LLN and > 25% decrease from BL
	Composite: > ULN and > 25% increase from BL
ALT	Absolute Value: > 3X ULN
	Absolute Value: > 5X ULN
	Absolute Value: > 8X ULN
AST	Absolute Value: > 3X ULN
	Absolute Value: > 5X ULN
	Absolute Value: > 8X ULN
ALT > 3X ULN and Tbili > 2X ULN	Composite: ALT > 3X ULN and Tbili > 2X ULN (with the Tbili elevation > 2 X ULN within 30 days of the ALT elevation > 3X ULN)
AST > 3X ULN and Tbili > 2X ULN	Composite: AST > 3X ULN and Tbili > 2X ULN (with the Tbili elevation > 2X ULN within 30 days of the AST elevation > 3X ULN)
CK	Absolute CK $\geq 2X$ ULN or 2X baseline value

Table 9: Pre-defined Limits of Change Criteria for Clinical Safety Laboratory Data (Continued)

Laboratory Test	Parameter for ANY Value and LAST Value
Hematology	
Hemoglobin	Male: absolute value \leq 11.5 g/dL
	Female: absolute value \leq 9.5 g/dL
	Change: \geq 2 g/dL decrease from BL
	Change: \geq 2 g/dL increase from BL
Platelets	Absolute value: \leq 75 x 10 ⁹ /L
	Absolute value: \geq 700 x 10 ⁹ /L
	Composite: > ULN and increase > 25% from BL
	Composite: < LLN and > 25% decrease from BL
White Blood Count	Composite: < LLN and > 25% decrease from BL
	Composite: > ULN and > 50% increase from BL
Eosinophils	Absolute value: > 10%

Abbreviations: BL = baseline; LDH = lactate dehydrogenase; LLN = lower limit of normal; PDLC = pre-defined limit of change; SGOT (AST) = serum glutamic oxaloacetic transaminase (aspartate aminotransferase); SGPT (ALT) = serum glutamic pyruvic transaminase (alanine aminotransferase); Tbili = total bilirubin; ULN = upper limit of normal

Supportive data listings for all laboratory results will be generated by laboratory type (hematology, serum chemistry, and urinalysis). Subject data listings will include the type of visit (eg, scheduled test, retest, or unscheduled), age, sex, laboratory test, test units, laboratory test result, and the laboratory standard normal ranges adjusted as appropriate for age and sex, if available. Laboratory values outside of the normal range will be flagged in the data listings.

Results of urine pregnancy tests will be presented in a listing only.

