Miglustat, dosed at 50 and 100 mg 3 times daily in subjects with Gaucher disease, exhibits dose-proportional pharmacokinetics. The pharmacokinetics of miglustat was not altered after repeated dosing 3 times daily for up to 12 months. In healthy subjects, co-administration of Zavesca[®] with food results in a decrease in the rate of absorption of miglustat (maximum observed concentration [C_{max}] in plasma was decreased by 36% and t_{max} was delayed for 2 hours) but had no statistically significant effect on the extent of absorption of miglustat (area under the plasma concentration-time curve [AUC] was decreased by 14%). The mean oral bioavailability of a 100-mg miglustat capsule is about 97% relative to an oral solution administered under fasting conditions. The pharmacokinetics of miglustat was similar between adult subjects with type I Gaucher disease and healthy subjects after a single dose administration of miglustat 100 mg (Zavesca Labeling-Package Insert 2014). The absolute bioavailability of miglustat was approximately 80% (Wraith and Imrie 2009).

Distribution: Miglustat does not bind to plasma proteins. Mean apparent volume of distribution of miglustat is 83 to 105 L in Gaucher patients. At steady state, the concentration of miglustat in cerebrospinal fluid of 6 subjects without Gaucher disease was 31.4% to 67.2% of that in plasma, indicating that miglustat crosses the blood-brain barrier (Zavesca Labeling-Package Insert 2014).

Metabolism and Excretion: The major route of excretion of miglustat is via kidney. Following administration of a single dose of 100 mg ¹⁴C-miglustat to healthy subjects, 83% of the radioactivity was recovered in urine and 12% in feces. In healthy subjects, 67% of the administered dose was excreted unchanged in urine over 72 hours. The most abundant metabolite in urine was miglustat glucuronide accounting for 5% of the dose. The $t_{1/2}$ of radioactivity in plasma was 150 hours, suggesting the presence of 1 or more metabolites with a prolonged half-life. The metabolite accounting for this observation has not been identified but may accumulate and reach concentrations exceeding those of miglustat at steady state. Miglustat did not inhibit or induce substrates of cytochrome P450 enzymes (Zavesca Labeling-Package Insert 2014).

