15.3.2.5. Safety Analyses

Safety analyses will be based the safety population. Safety data will be summarized using counts and percentages for categorical data and descriptive statistics (mean, standard deviation, median, minimum, maximum) for continuous data.

Exposure to study drug will be summarized using descriptive statistics.

Summaries of AEs will include an overall summary of incidence and summaries by relationship and by severity. Summaries and/or listings will be provided for deaths, SAEs, and AEs leading to discontinuation. Infusion-associated reactions in the ATB200/AT2221 arm will be compared in frequency to the alglucosidase alfa/placebo group in this study. Adverse events will be coded using Medical Dictionary for Regulatory Activities version 18 or higher.

Clinical laboratory results, ECG parameters, and vital signs will be summarized using descriptive statistics (number, mean, median, standard deviation, minimum, and maximum) by treatment group and visit for actual values and changes from baseline. The proportion of subjects with abnormalities will be provided for clinical laboratory results, ECGs, and vital signs. Shift tables will also be provided for clinical laboratory results.

Prior and concomitant medications and nondrug therapies will be summarized by treatment group. Concomitant medications terms will be coded using the World Health Organization Drug Dictionary (September 2013 DDE).

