APPENDIX 2. POTENTIALLY CLINICALLY SIGNIFICANT GUIDELINES

Criteria for identifying abnormalities as potentially clinically significant are based on the Guidelines for the Division of Neuropharmacological Drug Products, US Food and Drug Administration (revised on 2 April 1987). The laboratory values identified below are not inclusive of all the safety laboratory analytes that will be assessed during this clinical trial. Safety laboratory analytes that are known to be elevated in some adults with Pompe disease (eg, aspartate aminotransferase, alanine aminotransferase, lactate dehydrogenase) and safety laboratory analytes which are not listed below will be reviewed to determine if they are to be noted as potentially clinically significant based on the magnitude of the out of range value as compared to the normal range and the subject's baseline value, and whether the out of range value is coded as clinically significant by the principal investigator.

Laboratory Values		
Variable	Criterion Values	
	Standard Units	SI Units
Chemistry		
SGOT (AST)	≥ 3 x Upper Limit Normal	
SGPT (ALT)	≥ 3 x Upper Limit Normal	
Alkaline Phosphatase	≥ 3 x Upper Limit Normal	
LDH	≥ 3 x Upper Limit Normal	
BUN	≥ 30 mg/dL	≥ 10.7 μM
Creatinine	≥ 2.0 mg/dL	≥ 176.8 μM
Uric Acid	Male	≥ 10.5 mg/dL
	Female	≥ 8.5 mg/dL
		≥ 624.6 μM
		≥ 505.6 μM
Bilirubin (Total)	≥ 2.0 mg/dL	≥ 34.2 μM
Hematology		
Hematocrit	Male	≤ 37%
	Female	≤ 32%
Hemoglobin	Male	≤ 11.5 g/dL
	Female	≤ 9.5 g/dL
Platelets	≤ 75,000/mm ³ or ≥ 700,000/mm ³	≤ 75 x 10 ⁹ /L or ≥ 700 x 10 ⁹ /L
Leukocytes	≤ 2,800/mm ³ or ≥ 16,000/mm ³	≤ 2.8 x 10 ⁹ /L or ≥ 16 x 10 ⁹ /L
Eosinophils	≥ 10%	
Neutrophils	≤ 15%	
Urinalysis		
Protein	Increase of ≥ 2 units	
Glucose	Increase of ≥ 2 units	
Casts	Increase of ≥ 2 units	

Abbreviations: BUN = blood urea nitrogen; LDH = lactate dehydrogenase; SGOT (AST) = serum glutamic oxaloacetic transaminase (aspartate aminotransferase); SGPT (ALT) = serum glutamic pyruvic transaminase (alanine aminotransferase)

Vital Sign Values			
Variable	Criteria		Change Relative to Baseline
Heart Rate	≥ 120 bpm	and an	increase of ≥ 15 bpm
	≤ 50 bpm	and a	decrease of ≥ 15 bpm
Systolic Blood Pressure	≥ 180 mmHg	and an	increase of ≥ 20 mmHg
	≤ 90 mmHg	and a	decrease of ≥ 20 mmHg
Diastolic Blood Pressure	≥ 105 mmHg	and an	increase of ≥ 15 mmHg
	≤ 50 mmHg	and a	decrease of ≥ 15 mmHg
Weight			change of $\geq 7\%$ body weight

ECG Values		
ECG parameter	Low	High
PR interval (ms)	< 120 ms	≥ 210 ms

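### SAP Table 9 gives no threshold-based count by arm for nine analytes that have limits in Protocol Appendix 2, and SAP 9.2 omits the protocol's shift tables and abnormality proportions

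*SAP*

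**What the plan says.** **Protocol.** Section 15.3.2.5 states: "The proportion of subjects with abnormalities will be provided for clinical laboratory results, ECGs, and vital signs". It adds shift tables for laboratory results and does not restrict either output to selected analytes. Appendix 2 supplies numerical limits: "Criteria for identifying abnormalities as potentially clinically significant are based on the Guidelines for the Division of Neuropharmacological Drug Products". Alkaline phosphatase and LDH, for example, are each flagged at "≥ 3 x Upper Limit Normal".

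**SAP.** Section 9.2 gives the outlier count: "The percentage of subjects with specific treatment-emergent laboratory values that meet pre-defined limits of change (PDLC) will be summarized for these laboratory parameters". It continues: "The incidence rates of PDLC values will be compared descriptively between treatment groups, without any statistical testing". Table 9 holds the criteria, and its column heading applies them both to any value and to the last value. The same section says: "The set of laboratory parameters included in each table will correspond to those requested in the study protocol". It mentions neither shift tables nor a general proportion of subjects with abnormal results. The SAP Introduction (Section 2) says that the analyses it specifies take precedence over the protocol's.

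**The concern.** A reader of the protocol would expect an abnormality count by arm across the laboratory panel, with Appendix 2 as the natural source of limits. Under the SAP that count exists only for analytes with a Table 9 row, and the omitted rows include both renal chemistry markers for which the protocol sets limits.

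This is worth attention because AT2221 (miglustat) is given only in the experimental arm, and Protocol 6.2.1 says: "The major route of excretion of miglustat is via kidney". Albumin, calcium and sodium get an incidence comparison, while creatinine and BUN do not. At stake is how completely the safety comparison is reported. No efficacy result is touched.

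**Working it through.** The plan states no figure to reproduce here, so the check is a row-by-row comparison, followed by a search for any other count by arm.

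**Step 1. Appendix 2 against Table 9.**
- Appendix 2 lists 17 laboratory analytes.
- Eight have a Table 9 row: AST, ALT, bilirubin, uric acid, hemoglobin, platelets, leukocytes, eosinophils.
- 17 − 8 = 9 have none:

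| Analyte | Appendix 2 limit | Measured under |
|---|---|---|
| Creatinine | ≥ 2.0 mg/dL | Protocol Table 11 |
| BUN | ≥ 30 mg/dL | Protocol Table 11 |
| Alkaline phosphatase | ≥ 3 × ULN | Protocol Table 11 |
| LDH | ≥ 3 × ULN | Protocol Table 11 |
| Neutrophils | ≤ 15% | Protocol Table 12 |
| Hematocrit | ≤ 37% (men), ≤ 32% (women) | Protocol Table 12 |
| Urine protein | increase ≥ 2 units | Protocol Table 13 |
| Urine glucose | increase ≥ 2 units | Protocol Table 13 |
| Urine casts | increase ≥ 2 units | Protocol Table 13 (sediment microscopy) |

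- Table 9 adds seven analytes that Appendix 2 lacks: albumin, bicarbonate, calcium, phosphorus, potassium, sodium, CK. That makes 8 + 7 = 15 analytes in all, plus two combined transaminase and bilirubin criteria.
- The Table 9 footnote defines LDH although there is no LDH row.

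**Step 2. Is Appendix 2 a source for the SAP limits?** In part, it appears so. Table 9 repeats its absolute limits for uric acid (624.6 and 505.6 µM), hemoglobin (11.5 and 9.5 g/dL) and platelets (75 and 700 × 10⁹/L). SAP Table 10 repeats its heart-rate and blood-pressure limits, and SAP Table 11 its PR and QRS limits. Other rows differ, leukocytes for example, so Table 9 is not a plain copy.

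**Step 3. What else would show an outlier in the nine analytes?**
- *Adverse events.* Investigators judge out-of-range results with reference to Appendix 2 (Protocol 12.3.12.1). Those judged clinically significant are AEs (Protocol 13.1.1) and are counted by arm (SAP 9.1.2). This depends on judgement and not on a fixed limit.
- *Descriptive statistics by arm and visit.* The maximum shows how extreme the worst value was at a visit, but not how many subjects crossed a limit. Separate visit summaries cannot be combined into a count of subjects at any time.
- *Urinalysis.* Qualitative tests are categorized in summary tables, but the two-unit increase is not counted.
- *Listings.* Out-of-range values are flagged but not tallied.

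**Step 4. Units, in case the limits are copied.** SAP 9.2 presents laboratory data in SI units.
- BUN: 30 mg/dL = 300 mg/L. At 28 mg of nitrogen per mmol of urea, 300 / 28 = 10.7 mmol/L. Appendix 2 prints 10.7 with the unit µM.
- Creatinine: 2.0 × 88.4 = 176.8 µM, as printed.
- Uric acid: 10.5 × 59.48 = 624.5 and 8.5 × 59.48 = 505.6 µM, within 0.1 of the printed 624.6 and 505.6.

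Of the conversions checked, only BUN disagrees. The symbol should be confirmed in the original protocol file.

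**The case against.** The strongest reply is that these are two separate tools. Appendix 2 is a guideline for the investigator's judgement of clinical significance, and the protocol never says that it defines the analysis tables. Table 9 is a set of limits of change, with analytes and liver composites of its own, and choosing a different set is legitimate. This stands in part: identity with Appendix 2 was never promised. It does not explain the gap, because SAP 9.2 ties the parameters in its tables to the protocol's, Protocol 15.3.2.5 promises abnormality proportions without restricting analytes, and no reason is given for the nine omissions. For LDH, Appendix 2 does say that it can be elevated in Pompe disease, but it says the same of AST and ALT, which have rows.

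Four stronger readings are tempting, and the documents do not support them.
- *Outliers in these analytes are never counted by arm.* Clinically significant ones are, as TEAEs. Only CK, ALT and AST are blinded to investigators, and all three have Table 9 rows, so the AE route is open for the nine.
- *A few large rises would vanish in the arm means.* The summaries include the minimum and maximum, so an extreme value at a summarized visit would be visible. What is missing is the number of subjects.
- *The printed BUN unit would flag every subject.* Table 9 has no BUN row, so the unit affects no SAP count at present.
- *Renal excretion implies renal harm.* Protocol 6.2.1 describes how miglustat is eliminated and reports no renal signal. It helps to set priorities among the rows but is not evidence of a risk.

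**Conclusion.** The point holds as a gap in descriptive safety reporting. Nine of the 17 laboratory analytes with Appendix 2 limits have no threshold-based count by arm in the SAP, and the shift tables and abnormality proportions of Protocol 15.3.2.5 are absent from SAP 9.2 without explanation.

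The conclusion assumes that the SAP is followed as written. The SAP does not expressly withdraw the two protocol outputs, so a reader might infer either that they have been dropped or that they will still be produced. The documents settle neither. If they are produced, part of the gap closes, though counts against the Appendix 2 limits would still be unspecified.

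Nothing in the documents allows an estimate of how many subjects would go uncounted, so no size beyond the nine analytes can be given. Efficacy conclusions and type I error are unaffected. The change is worth making because it is cheap and the data are already collected.

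**What to change.** 1. Add rows to SAP Table 9 for the nine analytes, using the Appendix 2 limits and the table's existing any-value and last-value rule. Creatinine and BUN come first. If a row is left out on purpose, state the reason.
2. For LDH, consider adding a change-from-baseline condition, since Appendix 2 notes that it can be elevated in Pompe disease.
3. Write the BUN limit as 10.7 mmol/L (30 mg/dL), and correct or confirm the unit printed in Appendix 2.
4. Restore in SAP 9.2 the shift tables and the proportion of subjects with abnormal results named in Protocol 15.3.2.5, or record that they are withdrawn and why.

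The cost is some table rows and programming, with no new assessments. The downside is a longer descriptive table in which some imbalances will arise by chance. SAP 9.2 already specifies description without testing, and that should stay.

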Late-onset Pompe disease can present at any age greater than 12 months and does not present with clinically apparent cardiac involvement (Leslie and Bailey 2017). Late-onset Pompe disease is often referred to as juvenile-onset Pompe disease when occurring in the pediatric subpopulation of the LOPD category. Late-onset Pompe disease has a slower rate of progression compared with IOPD, with most patients experiencing progressive limb-girdle weakness and respiratory failure due to involvement of muscles in the proximal lower and upper limbs, paraspinal muscles, and diaphragm. Clinical manifestations include difficulty walking, climbing stairs, and progressive limitations of motor activities of daily living with progression to a need for ambulatory support followed by wheel chair dependence (Hirschhorn and Reuser 2001). Clinical manifestations of the disease are compounded by respiratory involvement, initially as sleep-disordered breathing and orthopnea (shortness of breath in supine position). The progressive nature of Pompe disease generally results in the use of invasive mechanically assisted ventilation. Biochemical abnormalities include increased level of serum creatine kinase (CK), a biomarker of muscle injury, and urinary hexose tetrasaccharide (Hex4), a biomarker of disease substrate. Life expectancy for patients with LOPD can range from early childhood to late adulthood, depending on the age of onset, rate of disease progression, the extent of respiratory muscle involvement, and the presence of co-morbidities (Hagemans et al 2004).

Enzyme replacement therapy (ERT) with recombinant human acid α -glucosidase (rhGAA), alglucosidase alfa, became available for all patients in Europe and the United States (US) in 2006. While alglucosidase alfa provides initial benefit to many patients, the magnitude and duration of therapeutic response with continuing therapy vary among individual patients (van der Ploeg et al 2010; Schoser et al 2017). The current ERT, at best, may offer improvement in measures of muscle function, strength and respiratory function for a finite duration followed by slow decline in these parameters (Toscano and Schoser 2013; Wyatt et al 2012).

In 2012, a systematic review of all studies performed in subjects with LOPD was performed by Toscano and Schoser 2013. This review included data on 368 subjects with LOPD from

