9.1. Treatment-emergent Adverse Events

Summary of adverse events will be based on TEAEs. A TEAE is defined as any event that started or changed in the severity on or after the first dose of study drug.

For AEs occurring on Day 1, if the start time of the event is missing or after the administration of the first dose of study drug, the event will be considered a TEAE.

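### The CK limit of change in SAP Table 9 joins an absolute and a baseline-relative limit with 'or', so its incidence can be dominated by CK that was already raised at baseline

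*SAP*

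**What the plan says.** SAP section 9.2 plans a summary, by treatment group, of the share of subjects with "specific treatment-emergent laboratory values that meet pre-defined limits of change (PDLC"). Table 9 sets the limits, and its column heading, "Parameter for ANY Value and LAST Value", applies them to any value and to the last one. The CK row reads "Absolute CK $\geq 2X$ ULN or 2X baseline value". The second limb has no printed operator; I read it as at least twice baseline.

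The SAP defines the term *treatment-emergent* only for adverse events, in section 9.1: "A TEAE is defined as any event that started or changed in the severity on or after the first dose of study drug". It gives no definition for laboratory values.

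Protocol section 6.1 says of the disease: "Biochemical abnormalities include increased level of serum creatine kinase (CK), a biomarker of muscle injury". Protocol section 6.3.1 reports that CK improved in all cohorts of the earlier ATB200/AT2221 study. For analytes known to be raised in some adults with Pompe disease (its examples are AST, ALT and LDH), Protocol Appendix 2 weighs the size of an out-of-range value "as compared to the normal range and the subject's baseline value".

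**The concern.** A table of limits of change should count subjects whose laboratory value changed. In the CK row, *or* leaves the ULN limb with no reference to baseline. A subject who enters with high CK from the disease and stays there, or improves without dropping below 2 times ULN, is counted beside one whose CK has doubled. The baseline limb has the reverse fault: it counts a doubling that never leaves the normal range.

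Most of Table 9 is built differently. Of the ten other single-analyte chemistry rows, seven (albumin, bilirubin, calcium, phosphorus, potassium, sodium, uric acid) include a composite limit that requires an out-of-range value and a change from baseline. Where bilirubin and uric acid also have an absolute limit, it stands on its own line. CK merges the two kinds of limit, so the output cannot show which one a subject met.

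At stake is the readability of the CK incidence. Real rises can be hidden among baseline elevations. A fall in CK on one arm, or a chance imbalance in baseline CK, also feeds into the comparison between arms.

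**Working it through.** The documents state no CK incidence or baseline CK distribution, so there is no figure to reproduce. The check has three parts.

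**1. The rule applied to single subjects** (CK in multiples of ULN; *b* = baseline, *v* = post-baseline).

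- As written: flag if *v* ≥ 2 or *v* ≥ 2*b*.
- Composite: flag if *v* ≥ 2 and *v* ≥ 2*b*, that is, *v* ≥ max(2, 2*b*).

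| b | v | change | as written | composite |
|---|---|---|---|---|
| 4 | 4 | 0% | flagged | no |
| 4 | 2.4 | −40% | flagged | no |
| 8 | 4 | −50% | flagged | no |
| 0.5 | 1.0 | +100% | flagged | no |
| 1.2 | 2.5 | +108% | flagged | flagged |
| 2.2 | 4.6 | +109% | flagged | flagged |

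This part needs no assumption. The composite limit is 2 times ULN when baseline is normal and 2 times baseline when baseline is above ULN.

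**2. How much of the count could be baseline disease.** From the Protocol (Table 10, Schedule of Assessments): 7 post-baseline chemistry visits (Weeks 2, 4, 6, 12, 26, 38, 52). All else is assumed: log-normal baseline CK with between-subject log-SD 0.7, within-subject log-SD 0.20 or 0.35, mean CK change 0% or −30%, the any-value rule, and 200,000 simulated subjects per scenario. Ranges run over the four combinations of noise and trend.

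| Assumed median baseline (× ULN) | flagged as written | of those, baseline already ≥ 2 × ULN | flagged by composite |
|---|---|---|---|
| 0.5 | 2–36% | 9–78% | 0–4% |
| 1 | 14–54% | 32–87% | 0–13% |
| 1.5 | 30–69% | 49–91% | 0–20% |
| 2 | 45–80% | 61–93% | 0–24% |
| 3 | 67–91% | 76–96% | 0–27% |

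Among subjects flagged as written, 2–12% have no post-baseline value above baseline when mean CK does not change, and 9–63% when it falls by 30%.

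**3. Whether a real signal would show.** Assume a median of 2.5 times ULN, between-subject log-SD 0.6 to 0.8, within-subject log-SD 0.2, and one true tripling of CK in 10% of subjects. The rate as written moves up by only about 2 percentage points from 74–80%. The composite rate moves from about 3% to about 12%.

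**The case against.** **A reader might infer that the count mostly reflects baseline disease.** The documents do not support that. The Protocol says only that CK is raised, not by how much. Under the assumptions above, the share exceeds half in every scenario only once the median reaches about 2 times ULN; below that it depends on noise and trend.

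**CK is not alone in ignoring baseline.** The ALT and AST rows use absolute limits only (above 3, 5 and 8 times ULN), although Appendix 2 names both as raised in some patients. This stands. What is particular to CK is that an absolute and a relative limit are merged into one count.

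***Treatment-emergent* could be programmed as not met at baseline.** That would remove stable and falling high values, and the SAP neither says nor excludes it. But a subject at 4 times ULN already meets the CK row at baseline, so the same reading would also drop a true rise from 4 to 9 times ULN. It does not rescue the single-row rule.

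**The sentence beginning "If a subject has even 1 post-baseline value that meets the PDLC criteria for any lab parameter" might be taken to fix the incidence count.** It governs which subjects' values are listed, not the percentage table.

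**A fall in CK might be thought visible only through this row.** It is not. CK is a pharmacodynamic endpoint with change and percent change by visit and a Week 52 comparison (SAP 8.8.6). SAP 9.2 summarises chemistry change by visit, and SAP 7.4 summarises baseline CK by arm. This limits the harm, though these outputs describe groups and do not count subjects with a rise.

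**A composite alone is insensitive.** It misses a rise from 4 to 7.9 times ULN. With an assumed median of 1.5 to 4 times ULN, between-subject log-SD 0.7 and within-subject log-SD 0.2, a true 75% rise in every subject is flagged at the last value in only 23–31%. This stands, and it is why the absolute limit should be kept on its own line.

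**Conclusion.** The point holds, and it is minor. As written, the CK row counts stable or falling CK at or above 2 times ULN, and doublings within the normal range, as limits of change. That follows from the text alone.

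The incidence *can* be dominated by baseline disease. The share of flagged subjects already at or above 2 times ULN runs from about 9% to 96% for assumed medians of 0.5 to 3 times ULN, and the documents cannot narrow this range.

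The consequence is confined to one row of a descriptive safety table that SAP 9.2 excludes from statistical testing. No efficacy result or error rate is affected, and CK change is reported elsewhere.

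**What to change.** Replace the CK row of SAP Table 9 with two lines, each applied to any value and to the last value:

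- Composite: ≥ 2X ULN and ≥ 2X baseline value
- Absolute value: ≥ 2X ULN

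Add one sentence to SAP 9.2: for laboratory limits of change, *treatment-emergent* means that the limit on that line was not already met at baseline. The composite line cannot be met at baseline, so it still catches doublings from a high starting value. The absolute line then counts subjects who newly cross 2 times ULN.

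The cost is one extra table line, one sentence and the matching program lines before database lock. The downside is that a rise of less than a doubling from a baseline already at or above 2 times ULN meets neither line; it remains visible in the laboratory listings and by-visit summaries. The new definition would also apply to the ALT and AST limits, so those tables should be checked when it is added.
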